# 6 Demographics and Baseline Characteristics

## 6.1 Subject Disposition

The number of subjects screened, enrolled, randomised and completing the study will be presented by treatment arm (i.e. test product, positive control, no treatment) and overall as well as in a separate summary, by treatment group (i.e. each right side of body/left side of body treatment combinations to which subjects were randomised) and overall using frequency counts and percentages.

## 6.2 Demographics

Age will be summarized descriptively using means, medians and standard deviations. Race and Fitzpatrick skin type scores will be summarised using frequency counts and percentages.

Document Name	Statistical Analysis CCI	207468.docx	
Type	Version	Document Identifier	Effective Date
eldo_clinical_doc	1.0; CURRENT; Most-Recent; Effective	090032d580d23463	10-Apr-2017 13:34:23
Reason For Issue	Auto Issue		

## 7 Treatment Compliance and Concomitant Medications

### 7.1 Treatment Compliance

All deviations associated with the application of either the test product or positive control or the preservation of the lack of treatment, if so assigned, to the relevant side of the face will be listed.

### 7.2 Concomitant Medications

Any concomitant medication use will be listed.

## 8 Analysis

The primary objective will be to evaluate the change from baseline in wrinkle dimensions in the crow's feet area for the test product compared to no treatment after 4 weeks of twice daily product application. Given that this is a POC study, the study will be considered a success if at least a trend in favour of the test product is observed. There will be no adjustment to the critical alpha level of 0.05 to account for inflation due to multiplicity. P-values resulting from inferential testing will be considered primarily as summary statistics.

### 8.1 Primary Analysis

The primary endpoint of the study will be change from baseline in Derma TOP parameter  $R_a$  at 4 weeks.

Baseline and change from baseline in DermaTOP parameters  $R_a$ ,  $R_z$ ,  $S_a$  and  $S_{tm}$  will be summarised (N, mean, standard deviation, median, minimum and maximum) by treatment arm (test product, Olay ProX Wrinkle Smoothing Cream, no treatment) for each study visit (weeks 2 and 4). For each parameter, test product versus no treatment and positive control versus no treatment will be compared for the change from baseline at 2 weeks, and 4 weeks, using analysis of covariance (ANCOVA) with subject (random effect), treatment, and side of face as main effects and baseline value as covariate. This approach allows for the inclusion of data from all subjects treated with a given treatment arm (test product, positive control or no treatment) regardless of the treatment group (test product/no treatment, test product/positive control, positive control/no treatment) to which they were randomised to derive estimates of treatment effect.

If the assumption of normality is rejected, an appropriate transformation to the data

Document Name	Statistical Analysis CCI	207468.docx	
Type	Version	Document Identifier	Effective Date
eldo_clinical_doc	1.0; CURRENT; Most-Recent; Effective	090032d580d23463	10-Apr-2017 13:34:23
Reason For Issue	Auto Issue		

may be performed to facilitate the above method of analysis. Least square means from the ANCOVA model for the change from baseline will be presented for each treatment arm and pairwise treatment comparisons, together with the 95% confidence intervals. In the absence of an appropriate data transformation, non-parametric analyses may be performed. In the event of the use of non-parametric analysis, median differences will be presented, together with 95% confidence intervals based on the Hodges-Lehmann method.

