3.4. Study Design and Dose Justification

This is a single-site, 3-arm, randomised, evaluator-blind, positive controlled (Olay ProX Wrinkle Smoothing Cream) and no-treatment controlled split-face POC study to evaluate the cosmetic appearance of fine lines and wrinkles provided by 4 weeks of

-

Document Name	Clinical Protocol 207468.doc		
Type	Version	Document Identifier	Effective Date
eldo_controlled	3.0; Most-Recent; Effective; CURRENT	090032d580d15804	24-Mar-2017 07:31:33
Reason For Issue	Auto Issue		

twice-daily application of the test product in healthy subjects presenting visible signs of ageing.

A split-face design has been selected to enable each subject to act as their own control. Subjects will be recruited to ensure they present the same wrinkle grades on both sides of their face at screening and baseline and a left-right treatment randomisation will be employed to ensure a consistent baseline between groups.

A positive control has been included in the design to help validate the trial results. Olay ProX Wrinkle Smoothing Cream has been selected as the positive control in light of favourable literature data concerning the wrinkle benefits of formulations containing similar cosmetic ingredients [Kaczvinsky 2009] and clinically proven claims made under the manufacturer.

It is hypothesised that the test product, which contains humectants to moisturise the SC, will help to reduce the appearance of fine lines and wrinkles caused by skin dryness. It is also hypothesised that by moisturising the skin and depositing lipids on the skin surface, that skin elasticity and barrier function will also be improved.

The application quantity of the study product(s) has been selected to reflect typical consumer usage of these types of products approximately 2 mg/cm² [Simion, 2006].

The inclusion criteria number 7, “Skin Type, of Visual Clinical Fitzpatrick Wrinkle Score Wrinkle Score 3-6 in the Periocular / Crow’s Feet Area ~~with an equal rating~~ on both sides of the face”, (a mild to moderate population for fine lines and wrinkles) has been selected based on clinical considerations to ensure a homogeneous population.

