9.3.2. Primary Analysis(es)

All efficacy analyses will be performed on the intent to treat (ITT) population.

Baseline and change from baseline in DermaTOP parameters R_a , R_z , S_a and S_{tm} will be summarised (N, mean, standard deviation, median, minimum and maximum) by treatment arm (test product, Olay ProX Wrinkle Smoothing Cream, no treatment) for each study visit (weeks 2 and 4). For each parameter, test product versus no treatment and positive control versus no treatment will be compared for the change from baseline at 2 weeks, and 4 weeks (primary endpoint), using analysis of covariance (ANCOVA) with subject (random effect), treatment, and side of face as main effects and baseline value as covariate. This approach allows for the inclusion of data from all subjects treated with a given treatment arm (test product, positive control or no treatment) regardless of the treatment group (test product/no treatment, test product/positive control, positive control/no treatment) to which they were randomised to derive estimates of treatment effect.

If the assumption of normality is rejected, an appropriate transformation to the data will be performed to facilitate the above method of analysis. Least square means from the ANCOVA model for the change from baseline will be presented for each treatment arm and pairwise treatment comparison, together with the 95% confidence intervals. In the absence of an appropriate data transformation, non-parametric analysis will be performed.

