### 4 Sample Size Determination

Approximately 90 healthy subjects will be screened to randomise at least 72 subjects to ensure 66 subjects complete the entire study. This will ensure approximately 44 subjects per treatment arm (test product, positive control, no treatment) or 22 per treatment group (test product/no treatment, test product/positive control, positive control/no treatment).

Document Name	Statistical Analysis CCI	207468.docx	
Type	Version	Document Identifier	Effective Date
eldo_clinical_doc	1.0; CURRENT; Most-Recent; Effective	090032d580d23463	10-Apr-2017 13:34:23
Reason For Issue	Auto Issue		

The sample size is based on clinical considerations. With 40 subjects, a difference between test product and untreated in the change from baseline in  $R_a$  of at least 46% of the magnitude of the within-subject standard deviation of the difference would be detectable at two-sided alpha=0.05 with approximately 80% power.

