# LSMean and standard error (SE) derived from ANCOVA with subject as random effect, treatment arm and side of face as fixed effects, and baseline value as covariate.

*Programmers Note: Same format for Tables 9.3.1.1, 9.3.1.3, 9.3.3.1, 9.3.4.1, 9.3.5.1 - Change the title, including adding the parameters as a BY group (DermaTOP has 4 parameters:  $R_a$ ,  $R_z$ ,  $S_a$  and  $S_{mb}$ , and Cutometer has 2 parameters: R5 and R7) to match protocol.*

 GlaxoSmithKline	Document Name	Statistical Analysis CCI 207468.docx		
	Type	Version	Document Identifier	Effective Date
	eldo_clinical_doc	1.0; CURRENT; Most-Recent; Effective	090032d580d23463	10-Apr-2017 13:34:23
	Reason For Issue	Auto Issue		

Protocol No. 207468

Page 1 of 2  
 Program Run Date:xxxx

Table 9.3.2.2  
 Analysis of TEWL Change from Baseline  
 ITT Population (N=xx)

Timepoint		Difference	95% Confidence Interval for the Difference	P-Value
Day 15	Moisturising Cream vs. No Treatment	X.XX	X.XX, X.XX	X.XXX
	Olay ProX Cream vs No Treatment	X.XX	X.XX, X.XX	X.XXX
	Moisturising Cream vs Olay Prox Cream	X.XX	X.XX, X.XX	X.XXX
Day 29	Moisturising Cream vs. No Treatment	X.XX	X.XX, X.XX	X.XXX
	Olay ProX Cream vs No Treatment	X.XX	X.XX, X.XX	X.XXX
	Moisturising Cream vs Olay Prox Cream	X.XX	X.XX, X.XX	X.XXX

Difference is the first named treatment adjusted (LS) mean change from baseline minus the second named treatment adjusted mean change from baseline.

Analysis model (ANCOVA) included subject as random effect, treatment arm and side of face as fixed effects, and baseline value as covariate.

***PROGRAMMER'S NOTE: Same format for Tables 9.3.1.2, 9.3.1.4, 9.3.3.2, 9.3.4.2, 9.3.5.2 - Change the title, including adding the parameters as a BY group (DermaTOP has 4 parameters: Ra, Rz, Sa and Stmp, and Cutometer has 2 parameters: R5 and R7) to match protocol.***

 GlaxoSmithKline	Document Name	Statistical Analysis CCI 207468.docx		
	Type	Version	Document Identifier	Effective Date
	eldo_clinical_doc	1.0; CURRENT; Most-Recent; Effective	090032d580d23463	10-Apr-2017 13:34:23
	Reason For Issue	Auto Issue		

Protocol No. 207468

Page x of y  
Program Run Date:xxxx

Table 9.3.6.1

Summary of Texture Rankings Based on USR-CliP Images  
ITT Population (N=xx)

Lay Reader ID		Moisturising Cream	Olay ProX Cream	No Treatment
1	N	XX	XX	XX
	Missing	XX	XX	XX
	Proportion Day 29 better than Baseline	X.XX	X.XX	X.XX
2	N	XX	XX	XX
	Missing	XX	XX	XX

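### The primary ANCOVA fits one baseline slope to both the between-subject and the left-right comparison; adding the subject's mean baseline would cost almost nothing and may sharpen the split-face contrast

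*SAP*

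**What the plan says.** Protocol 3.4 gives the reason for the design: "A split-face design has been selected to enable each subject to act as their own control". SAP 8.1 then specifies the primary model as "ANCOVA) with subject (random effect), treatment, and side of face as main effects and baseline value as covariate". Protocol 9.3.2 specifies the same model, with a random subject effect, fixed effects for treatment and "side of face as main effects and baseline value as covariate". The footnote to the SAP template for Table 9.3.2.2, which also serves the R_a tables, repeats it: "Analysis model (ANCOVA) included subject as random effect, treatment arm and side of face as fixed effects, and baseline value as covariate". SAP 8.2 carries the model over to the other change-from-baseline endpoints.

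Neither document adds a subject-mean baseline, a left-right baseline difference or separate slopes, and SAP 12 records no change to the planned analyses. Both sides are measured before any product is applied, so a subject mean can be derived from data already planned.

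**The concern.** With two sides per woman, baseline R_a carries two kinds of information. The average of the two sides says how wrinkled she is compared with other women. The difference between the sides says how uneven she is, and it includes any measurement or positioning error on either side. These two quantities need not predict change equally well. Error is a larger share of a difference between two similar readings than of their average, so the left-right difference may regress more strongly towards zero.

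A single slope in a random-intercept model is a weighted average of the two. It leans towards the between-subject slope when women differ from each other much more than the two sides of a face do. Where the slopes differ, the left-right baseline imbalance is then only partly removed. That comparison is the one the split-face design was chosen for, and it carries most of the information on test product versus no treatment.

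**Working it through.** **1. The plan's own figure.** SAP 4 bases power on 40 subjects and an effect of "at least 46% of the magnitude of the within-subject standard deviation of the difference", which "would be detectable at two-sided alpha=0.05 with approximately 80% power". For a paired t-test the noncentrality is 0.46 × √40 = 2.91. Power is 81.0% (82.9% by the normal approximation), and the effect detectable at 80% is 0.454 SD. The figure reproduces. It makes no use of baseline adjustment, so the slope question does not touch it.

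**2. The two slopes.** Assume equal variances at both visits. Let r_s be the correlation of R_a between sides at one visit, r_t that of the same side over time, and r_st that of opposite sides over time. Splitting each pair into its difference and its mean, the slopes of post-treatment value on baseline are:
- left-right: b_w = (r_t − r_st)/(1 − r_s)
- between subjects: b_b = (r_t + r_st)/(1 + r_s)

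The slope for change from baseline is the same minus 1. The two need not be equal. For correlations 0.7/0.8/0.65 (in the order r_s/r_t/r_st), b_w = 0.15/0.30 = 0.50 and b_b = 1.45/1.70 = 0.85.

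**3. What a blended slope leaves behind.** If the fitted slope is b, the left-right difference keeps extra variance of (b − b_w)² × Var(left-right baseline difference). A worked case uses assumed components: measurement SD 1, true side-level SD 0.5, between-subject SD 2, and change SD 0.5 at both side and subject level.
- Left-right slope of change: −1/(1 + 0.25) = −0.80.
- Between-subject slope of change: −0.5/(4 + 0.625) = −0.11.
- Slope fitted by the planned model in simulation: about −0.23.
- Variance of the left-right baseline difference: 2 × (0.25 + 1) = 2.5.
- Residual variance of the left-right difference in change, with its own slope: 2 × (0.25 + 1 + 1) − 0.80² × 2.5 = 2.90.
- With the blended slope: 2.90 + (0.80 − 0.23)² × 2.5 = 3.71, a ratio of 1.28.

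The simulated ratio for the whole treatment contrast, which also uses between-subject information, is 1.26.

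**4. Simulation over assumed correlations.** SAP 4 plans "This will ensure approximately 44 subjects per treatment arm (test product, positive control, no treatment) or 22 per treatment group", that is 66 completers in three pair groups. The design was simulated with sides balanced, a REML fit and 3,000 runs per scenario. SEs are empirical, for test product minus no treatment, in SD units of R_a. The last column takes the planned model's power as 80% and gives Φ(2.80 × SE ratio − 1.96).

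| r_s / r_t / r_st | b_w, b_b | SE planned | SE with subject mean | Variance ratio | Power |
|---|---|---|---|---|---|
| 0.8 / 0.8 / 0.75 | 0.25, 0.86 | 0.1127 | 0.1024 | 1.21 | 87% |
| 0.9 / 0.9 / 0.85 | 0.50, 0.92 | 0.0687 | 0.0643 | 1.14 | 85% |
| 0.8 / 0.85 / 0.75 | 0.50, 0.89 | 0.0966 | 0.0908 | 1.13 | 85% |
| 0.7 / 0.8 / 0.65 | 0.50, 0.85 | 0.1143 | 0.1099 | 1.08 | 83% |
| 0.6 / 0.8 / 0.5 | 0.75, 0.81 | 0.1001 | 0.1003 | 1.00 | 80% |
| 0.8 / 0.9 / 0.72 | 0.90, 0.90 | 0.0472 | 0.0473 | 0.99 | 80% |

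Over all 12 scenarios run, the ratio was 0.99 to 1.21 and type I error was 4.4-5.8% across both models. In sample-size terms, 40 subjects under the planned model match 40/1.08 ≈ 37 under the extended model at a ratio of 1.08, and 40/1.21 ≈ 33 at 1.21.

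**5. Simulation over assumed variance components.** Measurement SD is 1 and both change SDs are 0.5, with 1,200 runs per scenario. Entries are variance ratios, planned over extended.

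| Between-subject SD | True side-level SD 0 | 0.5 | 1 | 2 |
|---|---|---|---|---|
| 1 | 1.12 | 1.05 | 1.01 | 0.99 |
| 2 | 1.41 | 1.26 | 1.06 | 1.02 |
| 3 | 1.49 | 1.30 | 1.11 | 1.03 |

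The result depends heavily on measurement error. With between-subject SD 3 and the true left-right difference given an SD of 1, the excess is about 24% at measurement SD 1 and about 6% at measurement SD 0.5. It is about 2% if both change SDs are then raised to 1.

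**The case against.** The planned model is a standard split-face ANCOVA, fully specified and stated consistently in both documents. Nothing in it is wrong. Randomisation protects the estimate, and the simulations show type I error close to nominal. All of that stands.

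The size of the gain is also open. The documents report no SD, reliability or correlation for R_a, and the DermaTOP procedure that would bear on repeatability is redacted. Two features of the protocol point towards a smaller gain. Entry is limited to wrinkle scores 3-6 to obtain a homogeneous population (3.4), which may narrow between-subject spread. Inclusion criterion 7b as amended no longer asks for equal ratings on the two sides, so real left-right asymmetry is possible. The secondary endpoints may have quite different noise structures. Finally, this is a proof-of-concept study whose success criterion is a trend, with p-values used mainly as summaries (SAP 8), so a few points of power will seldom decide the outcome.

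These arguments limit the claimed benefit. They do not make the change costly: the largest simulated loss was about 1% of variance. A trend criterion also rests on the point estimate, so its precision still matters. Other analyses would separate the slopes too, such as paired differences with a baseline-difference covariate. The extra covariate is simply the smallest departure from the plan.

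**Conclusion.** The point holds as a low-cost efficiency improvement, conditional on the two slopes differing. On assumed inputs the gain is nil to about 20% of the variance of the primary contrast under moderate assumptions, or 0 to 7 points of power from a base of 80%. In the component scenarios it is 26-30% when measurement SD is twice the true side-level SD and between-subject SD is 2-3. It reaches about 35-50% only when left-right baseline differences are almost all measurement noise and between-subject spread is large. It is essentially nil when the slopes are close or measurement error is small.

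A reader might infer more: that the planned analysis is biased, that the stated 80% power is wrong, or that a third or more of the precision is being lost. The documents support none of these. The estimate is unbiased, the power figure reproduces for 40 pairs, and the large losses come from inputs that the documents do not give. Whether 40 pairs is the right count for a design with 22 direct test/no-treatment pairs is a separate question. Nor has a gain been shown for the secondary endpoints, since the calculations concern the R_a contrast.

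**What to change.** Before unblinding, amend SAP 8.1 to include two baseline covariates: the side-specific value and the subject's mean of the two sides. The side-specific term then estimates the left-right slope, and the subject mean absorbs the difference between the two slopes. Update the footnotes of the Table 9.3.2.1 and 9.3.2.2 templates, which serve all the ANCOVA tables, and record the departure from protocol 9.3.2 in SAP 12. Use the same model for the SAP 8.2 ANCOVAs for consistency, without claiming a gain there.

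The cost is one sentence, one model term and one degree of freedom out of about 62, or about 1% of variance at most. No new data are needed. If the blind has already been broken, the extended model should be reported only as a labelled sensitivity analysis, so that it is not a post hoc choice of primary model.

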## 8.2 Secondary Analysis

The same presentation and analysis methods, as outlined above, will be performed using change from baseline for other parameters; DermaTOP parameters Rz, Sa and Stm, clinical wrinkle assessment, TEWL values, Corneometer values and Cutometer parameters R5 and R7.

The texture assessment resulting from the ranking of photos will inherently be an assessment of change from baseline. As such, the data resulting from these rankings will be tabulated by treatment arm as proportions with baseline image better and Day 29 image better and analysed using a logistic regression with effects for treatment arm and side of face included in the model.

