6.2.1 USR- CliP High Resolution Images

CCI	

Document Name	Clinical Protocol 207468.doc		
Type	Version	Document Identifier	Effective Date
eldo_controlled	3.0; Most-Recent; Effective; CURRENT	090032d580d15804	24-Mar-2017 07:31:33
Reason For Issue	Auto Issue		

CCI

Informed consent will be sought from the subjects for the use of photographs taken of their face during this study and for the purpose of Ad-hoc analysis by the sponsor company.

[figure not shown]
After the study has completed, all of the high resolution images will be assessed by 24 lay raters at one time to evaluate texture (pores, smoothness and unevenness).

The lay raters will come to the study site on image assessment days and will be informed about the assessment and will give their written informed consent to participate, which includes the following inclusion/exclusion criteria (Inclusion: 18 to 70 years; knowledge how to use a computer, Exclusion: problems with the eyes; change of lenses or glasses within the last 7 days before the start of the study; migraine or headache on the assessment day). CCI

The 24 lay raters will be recruited from ProDERMs database. Once the 'rater' Informed Consent is signed, proDERM are to explain the imaging assessment process (2 images on the same screen that have to ranked), and how the scale works and how the subjects are to use the software.

CCI

Document Name	Clinical Protocol 207468.doc		
Type	Version	Document Identifier	Effective Date
eldo_controlled	3.0; Most-Recent; Effective; CURRENT	090032d580d15804	24-Mar-2017 07:31:33
Reason For Issue	Auto Issue		

CCI

[figure not shown]
CCI

CCI

CCI

[figure not shown]

CCI

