	Proportion Day 29 better than Baseline	X.XX	X.XX	X.XX
etc		XX	XX	XX
24	N	XX	XX	XX
	Missing	XX	XX	XX
	Proportion Day 29 better than Baseline	X.XX	X.XX	X.XX
Total	N	XX	XX	XX
	Missing	XX	XX	XX
	Proportion Day 29 better than Baseline	X.XX	X.XX	X.XX
	95%CI	X.XX, X.XX	X.XX, X.XX	X.XX, X.XX

 GlaxoSmithKline	Document Name	Statistical Analysis CCI 207468.docx		
	Type	Version	Document Identifier	Effective Date
	eldo_clinical_doc	1.0; CURRENT; Most-Recent; Effective	090032d580d23463	10-Apr-2017 13:34:23
	Reason For Issue	Auto Issue		

Protocol No. 207468

Page x of y  
 Program Run Date:xxxx

Table 9.3.6.2  
 Analysis of Texture Rankings Based on USR-CliP Images  
 ITT Population (N=xx)

Timepoint	Difference in Proportions of Day 29 Image Better than Baseline	95% Confidence Interval for the Difference	P-Value
Moisturising Cream vs. No Treatment	X.XX	X.XX, X.XX	X.XXX
Olay ProX Cream vs No Treatment	X.XX	X.XX, X.XX	X.XXX
Moisturising Cream vs Olay ProX Cream	X.XX	X.XX, X.XX	X.XXX

Difference is the first named treatment minus the second named treatment.

Analysis model (logistic regression) included treatment arm and side of face as fixed effects.

Document Name	Statistical Analysis CCI	207468.docx
Type	Version	Document Identifier
eldo_clinical_doc	1.0; CURRENT; Most-Recent; Effective	090032d580d23463
Reason For Issue	Auto Issue	10-Apr-2017 13:34:23

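### The texture logistic regression ignores clustering by image pair and subject and gives no unit of analysis; if the 24 raters' choices are pooled, its intervals are too narrow.

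*SAP*

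**What the plan says.** SAP 8.2 tabulates, by treatment arm, how often the baseline or the Day 29 image was judged better, and says the data will be "analysed using a logistic regression with effects for treatment arm and side of face included in the model". The footnote to the Table 9.3.6.2 shell (SAP Appendix 3) repeats this: "Analysis model (logistic regression) included treatment arm and side of face as fixed effects". That table reports, for three treatment comparisons, the "Difference in Proportions of Day 29 Image Better than Baseline" with a 95% confidence interval and p-value. Protocol 9.3.3 names logistic regression without listing any terms.

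On the rating task, Protocol 6.2.1 says that "all of the high resolution images will be assessed by 24 lay raters at one time to evaluate texture", with "2 images on the same screen that have to ranked". Protocol 5.8.1 gives each rater a separate presentation order, so raters are crossed with image pairs. SAP 3 randomises each subject to two of the three arms, one per side of the face.

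The shell of Table 9.3.6.1, "Summary of Texture Rankings Based on USR-CliP Images", has rows for raters 1 to 24, each with N and a proportion, followed by a Total with N, a proportion and a 95% CI.

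For the continuous endpoints, SAP 8.1 does allow for the split face, "using analysis of covariance (ANCOVA) with subject (random effect), treatment, and side of face as main effects and baseline value as covariate".

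**The concern.** Twenty-four judgements of the same two photographs are not 24 independent observations, and the two halves of one face are not independent either. A logistic regression with only arm and side treats every record as independent. How much this matters, and in which direction, depends on what a record is, and the SAP does not say. If each record is one rater's choice, agreement about a given image pair inflates the apparent sample size, so the reported interval and p-value for test product versus no treatment overstate precision. If each record is one summary result per image pair, the rater problem disappears. What remains is the ignored left-right pairing, which makes the interval too wide when the halves are positively correlated.

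**Working it through.** The plan's only power statement concerns R_a (40 subjects, 46% of the SD of the within-subject difference, two-sided 0.05, about 80%). An exact paired t-test gives 81.0%, so it reproduces. No size, power or precision is stated for texture.

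**Inputs**
- SAP 4: "Approximately 90 healthy subjects will be screened to randomise at least 72 subjects to ensure 66 subjects complete the entire study". This means 22 subjects per treatment pair and 44 half-faces per arm for 66 completers, or 24 and 48 if all 72 complete. Imaging needs separate consent (Protocol 3.1 and 6.1.2), so these are upper figures.
- 24 raters (Protocol 6.2.1).
- Assumed, because the documents give no agreement figure: rho, the correlation of choices within an image pair, 0.01 to 0.20; rho_b, the correlation of choices between the two halves of one face, from 0 to rho.

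**Pooled reading.** Let k be the subjects per treatment pair. Each arm has 2k half-faces and 48k ratings: 1,056 for k = 22, 1,152 for k = 24. In units of p(1 - p):
- model variance of the difference = 2/(48k)
- true variance of each arm mean = (1 + 23 rho)/(48k)
- covariance of the two arm means, through the k subjects who carry both treatments = k rho_b/(2k)^2 = rho_b/(4k)
- true / model variance = 1 + 23 rho - 12 rho_b, whatever k is

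Type I error of the nominal 5% test = 2 x Phi(-1.96 / SE ratio). In each range the first value takes rho_b = rho and the second rho_b = 0.

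| rho | Variance ratio | SE ratio | Type I error |
|---|---|---|---|
| 0.01 | 1.11 to 1.23 | 1.05 to 1.11 | 6.3% to 7.7% |
| 0.05 | 1.55 to 2.15 | 1.24 to 1.47 | 11.5% to 18.1% |
| 0.10 | 2.10 to 3.30 | 1.45 to 1.82 | 17.6% to 28.1% |
| 0.20 | 3.20 to 5.60 | 1.79 to 2.37 | 27.3% to 40.8% |

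Half-width of the 95% CI at p = 0.5: 1.96 x sqrt(0.5/1056) = 4.3 percentage points. At rho = 0.05 it should be 4.26 x 1.245 = 5.3 to 4.26 x 1.466 = 6.3 points. With 1,152 ratings, 4.1 should be 5.1 to 6.0.

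**Simulation check.** Trials were simulated with no treatment effect, 66 subjects, crossed raters and 2,000 runs per scenario. With nothing shared between halves, rho of 0.049 and 0.099 gave SE ratios of 1.42 and 1.79 (formula 1.47 and 1.81) and type I error of 17.6% and 26.5%. The same model with subject-clustered standard errors gave 4.0% to 6.8% over all 45 scenarios.

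**Rater leniency.** If raters differ in leniency with variance share rho_r, the SE ratio becomes sqrt(1 - rho_r + 23 rho - 12 rho_b). At rho = 0.008 and rho_r = 0.17 this is sqrt(1.014) = 1.01 with rho_b = 0 and sqrt(0.918) = 0.96 with rho_b = rho (simulated 1.01 and 0.97). The inflation vanishes there.

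**Total CI in Table 9.3.6.1.** If it is a simple binomial interval on pooled ratings (the method is not stated), its coverage is 2 x Phi(1.96 / sqrt(1 + 23 rho)) - 1: about 92%, 82%, 72% and 59% at the four values of rho.

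**One result per pair.** With correlation r between the two halves' results, true / model variance = 1 - r/2. At r = 0, 0.2 and 0.5 the SE ratio is 1.00, 0.95 and 0.87, so the interval is 0%, 5% or 15% too wide, with type I error 5.0%, 3.9% or 2.4%. The model half-width at p = 0.5 is 1.96 x sqrt(0.5/44) = 20.9 points.

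The same SAP sentence therefore permits a half-width of 4.3 or 20.9 points, a factor of sqrt(24) = 4.9, depending on an unstated choice.

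**The case against.** The strongest objection is that the narrow intervals depend entirely on pooling, which the documents never state. Protocol 6.2.1 is redacted around the rater procedure, the Appendix 4 ranking scale is a missing figure and some SAP pages were removed, so a rule for combining the 24 choices may exist. Table 9.3.6.1 is descriptive and does not fix the input to the model in Table 9.3.6.2. This stands, and it is why the direction of the error is conditional. However, SAP 8.2 and both texture shells are legible, name no such step and leave the unit open.

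Second, the error in the other direction can exceed 15%. If the halves share fully, a simulated majority vote gives r of about 0.53 at rho = 0.10 and 0.68 at rho = 0.20, so the interval is 1/sqrt(1 - r/2), or about 17% to 23%, too wide. That is correct; it strengthens the case for clustering on subject.

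Third, rho is assumed. Also true: the sizes are a range, not an estimate.

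Finally, little depends on this test. Texture is not in the topline tables (SAP 11), the named key secondary is the Fitzpatrick wrinkle score (SAP 5.1), and SAP 8 reads p-values mainly as summary statistics. That limits the consequence, but a reported interval should still describe its own uncertainty correctly.

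**Conclusion.** The concern holds. The stated texture model has no clustering term, and the legible plan does not define its unit of analysis. Pooling is the likelier reading, not a certain one. Under pooling the SE is understated by a factor of 1.05 to 2.37 for assumed rho between 0.01 and 0.20, except in a narrow corner of very low agreement combined with large differences in rater leniency. With one result per pair the interval is correct if the halves are uncorrelated and otherwise too wide, by 5% to about 23% at the correlations considered. The primary R_a analysis and the success rule are unaffected. The SAP should be corrected, in proportion to one secondary endpoint of a proof-of-concept study.

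**What to change.** In SAP 8.2 and the Table 9.3.6.2 footnote:
- State the unit of analysis, for example one rater's choice for one half-face image pair.
- Keep the logistic model with arm and side, fitted by GEE or with robust standard errors clustered on subject. Because both halves belong to one subject, this covers the image pair and the split face, and it also suits one result per pair.
- Derive the difference in proportions and its 95% CI from the model's predicted probabilities by the delta method (simulated coverage 93.2% to 96.0%).

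For Table 9.3.6.1, state how the Total CI is computed and cluster it on the half-face. Say that both intervals apply to the 24 raters used; generalising to other raters would need a random rater effect.

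The cost is SAP wording and one model statement, with no new data, and the protocol's logistic regression is kept. If ratings are pooled, the texture intervals will probably be wider. With 66 to 72 clusters the robust test is close to nominal but not exact.
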